4.1.2 Exclusion Criteria

Patients who meet any of the following criteria will be excluded from study entry:

- Any prior treatment for primary invasive breast cancer
- Patients with cT4 or cN3 stage breast tumors
- Metastatic (Stage IV) breast cancer
- Bilateral invasive breast cancer
- Multicentric breast cancer (the presence of more than one tumor in different quadrants of the breast)
- Patients who have undergone excisional biopsy of primary tumor and/or axillary lymph nodes
- Patients who have undergone sentinel lymph node biopsy prior to study treatment
- Type 1 or 2 diabetes requiring antihyperglycemic medication
- Inability or unwillingness to swallow pills
- Malabsorption syndrome or other condition that would interfere with enteric absorption
- History of prior or currently active small or large intestine inflammation (such as Crohn's disease or ulcerative colitis)
- Congenital long QT syndrome or QT interval corrected using Fridericia's formula (QTcF) > 470 msec

- Clinically significant (i.e., active) cardiovascular disease, like uncontrolled hypertension, unstable angina, history of myocardial infarction, cardiac failure class II-IV (New York Heart Association, [Appendix 5](#)), or any other that in the judgment of the investigator could jeopardize patient safety or study outcomes
- Any contraindication to MRI examination, including the following:
 - Neurostimulators
 - Pacemakers
 - Implanted metallic material or devices (metal implants or large tattoos in the field of view)
 - Severe claustrophobia
 - Physical characteristics (weight and/or size) that exceed the capabilities of the MRI scanner
 - Known allergy or hypersensitivity reactions to gadolinium, versetamide, or any of the inert ingredients in gadolinium-based contrast agents
 - Severe renal insufficiency, e.g., estimated glomerular filtration rate < 30 mL/min
- Active infection requiring intravenous (IV) antibiotics
- Patients requiring any daily supplemental oxygen
- Clinically significant history of liver disease, including viral or other known hepatitis, current alcohol abuse, or cirrhosis
- Known human immunodeficiency virus (HIV) infection
- Any other diseases, active or uncontrolled pulmonary dysfunction, metabolic dysfunction, physical examination finding, or clinical laboratory finding giving reasonable suspicion of a disease or condition that contraindicates the use of an investigational drug, that may affect the interpretation of the results, or renders the patients at high risk from treatment complications
- Significant traumatic injury within 3 weeks prior to initiation of study treatment
- Major surgical procedure within 4 weeks prior to initiation of study treatment
- Inability to comply with study and follow-up procedures
- History of other malignancy within 5 years prior to screening, except for appropriately treated carcinoma in situ of the cervix, non-melanoma skin carcinoma, or Stage I uterine cancer

4.2 METHOD OF TREATMENT ASSIGNMENT AND BLINDING

4.2.1 Patient Randomization

After written informed consent has been obtained and eligibility has been established, the study site will obtain a patient's identification number and treatment assignment using a permuted block randomization algorithm via an interactive voice or web-based response system (IxRS).

4.2.2 Stratification

Patients will be randomized into one of the two treatment arms in a 1:1 ratio based on the following stratification factors:

- Tumor size (T1-2 vs. T3)
- Nodal status (cytologically positive vs. radiologically or cytologically negative). If on ultrasound examination there is evidence of suspicious axillary lymph nodes at the baseline examination, then fine needle aspiration (FNA) or core biopsy is required to confirm nodal status.

4.2.3 Blinding

Investigators and patients will be blinded to treatment assignment of GDC-0032 or placebo.

If unblinding is necessary for patient management (e.g., in the case of a serious adverse event for which patient management might be affected by knowledge of treatment assignment), the investigator will be able to break the treatment code by contacting the IxRS following approval from the Medical Monitor. Treatment codes should not be broken except in emergency situations where unblinding is needed for treatment decisions. Effort should be made to contact the Medical Monitor before unblinding. Patient treatment assignment may be unblinded at the time the patient discontinues from the blinded treatment phase at the request of the treating physician by contacting the IxRS following approval from the Medical Monitor and stating the reason for unblinding. Unblinding during the study will result in the withdrawal of a patient from the study. For regulatory reporting purposes, and if required by local health authorities, the Sponsor will break the treatment code for all serious, unexpected, suspected adverse reactions that are considered by the investigator or Sponsor to be related to study drug.

While PK samples must be collected from patients assigned to the comparator arm to maintain the blinding of treatment assignment, PK assay results for these patients are generally not needed for the safe conduct or proper interpretation of this trial. The PK assay group will be unblinded to patients' treatment assignments to identify appropriate PK samples to be analyzed and bioanalytical methodology to employ. However, the PK scientist does not have access to the PK assay results and therefore stays blinded until the PK assay results need to be interpreted and reported. Samples from patients assigned to the comparator arm will be analyzed for letrozole. However, GDC-0032 assay will be analyzed by request (i.e., to evaluate a possible error in dosing).

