3.1.1 Surgery

Surgery will take place after at least 16 weeks of treatment, during Weeks 17 – 18. Surgery should be performed within 4 days after the last dose of GDC-0032, if possible, to best observe pharmacodynamic knockdown with GDC-0032 in the surgical specimen. Surgery may be delayed due to toxicity or other safety issues, upon discussion with the Medical Monitor (see [Section 5.4.1](#)) or recommendations from the Independent Data Monitoring Committee (IDMC; see below). A maximum of 16 weeks of GDC-0032 can be administered. Letrozole can be continued up to surgery per the investigator’s discretion.

Breast and axillary surgery will follow local practice. However, pre-surgical SLNB is not allowed. Information on the type of surgery will be collected and recorded. Surgery specimens will be collected for histological examination to assess for pCR and for other endpoint analyses.

Following surgery, follow-up will proceed according to local standards of care. Adjuvant endocrine therapy and/or chemotherapy will be delivered as per the investigator's choice. Postoperative radiotherapy is required if BCS is performed. In the event of mastectomy, radiotherapy is to be administered according to local guidelines.

A postsurgery visit will be performed 4 weeks (+ 1 week) after surgery, and will mark the end of the study. Assessment of adverse events and general safety will be collected at this visit and the plan for future treatment will be recorded.

The patient should be evaluated at baseline and after Week 13 of treatment for planning of the surgical procedure (BCS or mastectomy), and both physician recommendation and final patient decision should be documented in the electronic Case Report Form (eCRF).

The co-primary efficacy endpoint, pCR (pCR–ypT0/is, ypN0) will be established via a local review following completion of neoadjuvant therapy and surgery.

Please refer to the pathology manual for further guidance of evaluation for pCR and directions for sending a copy of the pathology report.

A schedule of assessments is provided in [Appendix 1](#).

An Independent Review Facility (IRF) will be used to determine the tumor ORR via MRI. IRF procedures are detailed in the IRF charter.

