6.4.1 Primary Efficacy Endpoint

The co-primary efficacy endpoints are (1) tumor ORR, assessed by modified RECIST criteria by breast MRI and (2) the rate of pCR in breast and axilla (total pCR) after completion of study drug.

The tumor ORR will be calculated by treatment arm in all enrolled population and in *PIK3CA* MT population. Within each population, the ORR for the two treatment arms will be compared at a two-sided alpha of 16% using a Cochran Mantel-Haenszel test, stratified by tumor size and nodal status. The pCR rate will also be calculated and compared at a two-sided alpha of 4% based on the same analytical approach as ORR. The two alpha values account for a family-wise type I error rate of 20%. Patients with early study termination and hence missing efficacy outcome will be considered as non-responders.

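### Section 4.2.3 makes any unblinding end study participation, which can create missing co-primary outcomes that 6.4.1 scores as non-response, and its rules on non-emergency code-breaks before the locally read pCR conflict

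*Protocol*

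**What the plan says.** Section 4.2.3 (Blinding) contains four rules that bear on this point.

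- The consequence of a code-break: "Unblinding during the study will result in the withdrawal of a patient from the study". No exception is given, and the exit is from the study, not from study drug. Elsewhere the protocol keeps these apart: 4.6.1 covers leaving the study and 4.6.2 covers stopping treatment.
- The general limit: "Treatment codes should not be broken except in emergency situations where unblinding is needed for treatment decisions".
- A further route: "Patient treatment assignment may be unblinded at the time the patient discontinues from the blinded treatment phase at the request of the treating physician", which is available "following approval from the Medical Monitor and stating the reason for unblinding".
- Regulatory reporting: "the Sponsor will break the treatment code for all serious, unexpected, suspected adverse reactions", where required by local authorities. This comes directly after the withdrawal sentence, with nothing to say that the withdrawal rule does not apply to it.

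On analysis, 6.4 is intention-to-treat over all randomised patients, and 6.4.1 adds: "Patients with early study termination and hence missing efficacy outcome will be considered as non-responders".

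On timing, the MRI for the co-primary ORR is in Week 16 (3.1) and is read centrally. GDC-0032 or placebo is given for at most 16 weeks. "Surgery will take place after at least 16 weeks of treatment", in Weeks 17–18, and pCR "will be established via a local review following completion of neoadjuvant therapy and surgery" (3.1.1).

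**The concern.** A code-break before Week 16 removes the patient before the MRI and the surgical pathology. The protocol would then itself create the missing outcome that it scores as failure. Section 4.2.3 gives a serious adverse event as its example of a reason to unblind. Section 1.7.1 reports drug-related Grade 3–4 diarrhea in 11% of 27 patients on daily GDC-0032 plus letrozole. It is therefore plausible that more code-breaks would occur on GDC-0032 than on placebo. In that case toxicity is partly recorded as lack of response on the co-primary endpoints.

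Separately, a code-break that is not an emergency can occur after blinded treatment ends and before a co-primary endpoint is judged locally. The paragraph that allows this also restricts code-breaks to emergencies and orders the unblinded patient out of the study. A site cannot tell from the text what should happen to her pCR.

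**Working it through.** **Which outcomes a code-break can affect**

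| Time of code-break | MRI ORR | pCR |
|---|---|---|
| Before the Week 16 MRI | may be missing | may be missing |
| After the MRI, before pathology is read | already observed | missing, or obtained after the arm may be known at the site |
| After pCR is recorded | observed | observed |

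For a patient who completes treatment, the physician-requested route opens in the second row. Her pCR is then either missing and scored as non-response, or recovered and read locally after unblinding. Only one of these can apply to one patient, and the protocol does not say which.

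**Reproducing the plan's figure (6.1)**

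Inputs for ORR in the mutant cohort: 40% vs 64%, two-sided alpha 16% (z = 1.405), power 80% (z = 0.842), allocation 40:60 (control n₁, k = 1.5), chi-square with continuity correction.

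- Pooled rate: (0.40 + 1.5 × 0.64)/2.5 = 0.544.
- Uncorrected n₁ = [1.405·√(0.544·0.456·1.667) + 0.842·√(0.24 + 0.2304/1.5)]² / 0.24² = 35.6.
- Corrected n₁ = (35.6/4)·[1 + √(1 + 2·1.667/(35.6·0.24))]² = 42.2, so 43, and 43 × 2.5 gives 108 in total. The plan states 108.
- The same method for pCR (1% vs 19%, alpha 4%) gives 123, against the stated 120 (within 3%).

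**Choice of denominator**

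The 108 already excludes the 10% assumed unevaluable for MRI. A patient scored as a non-responder stays in the analysis, so the relevant cohort is the 120 (n₁ = 48 control, 72 GDC-0032).

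**Effect of the rule**

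The protocol gives no unblinding rate. *Assumed* range: 2–10% on GDC-0032 and 0–2% on placebo, all before the MRI, all with outcome missing, and no other missing data. Each response rate is multiplied by (1 − share unblinded). With d the resulting difference:

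- Effective control n after the correction: m = (n₁ − 1.667/(2d))²/n₁.
- Power = Φ[(d − 1.405·SE₀)/SE₁], with SE₀ pooled and SE₁ unpooled, both on m and 1.5m.

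Worked results:

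- 0%/0%: d = 0.64 − 0.40 = 0.240; m = (48 − 3.47)²/48 = 41.3; SE₀ = 0.1000, SE₁ = 0.0976; Φ(1.019) = 84.6%.
- 2%/0%: d = 0.6272 − 0.400 = 0.227; m = 40.9; SE₀ = 0.1006, SE₁ = 0.0983; Φ(0.873) = 80.9%.
- 5%/1%: d = 0.608 − 0.396 = 0.212; m = 40.5; SE₀ = 0.1014, SE₁ = 0.0992; Φ(0.701) = 75.8%.

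| GDC-0032 / placebo unblinded | ORR difference | ORR power | pCR power |
|---|---|---|---|
| 0% / 0% | 24.0 points | 84.6% | 79.1% |
| 2% / 0% | 22.7 | 80.9% | 77.6% |
| 5% / 1% | 21.2 | 75.8% | 75.2% |
| 10% / 2% | 18.4 | 65.2% | 71.0% |

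**Direction under no true effect**

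With ORR 40% in both arms, 5%/0% gives 0.40 × 0.95 − 0.40 = −2.0 points, and 10%/2% gives 0.36 − 0.392 = −3.2 points. The shift is against GDC-0032.

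**The case against.** Several stronger conclusions are tempting, and the protocol does not support them.

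- *Every withdrawn patient is scored a non-responder.* Section 6.4.1 makes the missing outcome a condition. An MRI done before unblinding still counts. Section 4.6.1 asks for every effort to obtain information on patients who leave, and bars follow-up only after consent is withdrawn; unblinding is not withdrawal of consent.
- *Safety follow-up is lost.* Sections 5.1, 5.3.1 and 5.5.1 keep adverse event reporting and follow-up going for at least 30 days after the last dose, and continue it for ongoing treatment-related events in patients who leave. At most the scheduled post-surgery visit is at risk.
- *All locally read endpoints are exposed.* Palpation, ultrasound and mammography are done at the Week 16 visit, so for completers they come at or before the point where the physician-requested route opens. The MRI is read centrally. The exposure is mainly to pCR.
- *Unblinding is available on demand.* The physician-requested route needs Medical Monitor approval and a stated reason.
- *Regulatory code-breaks remove patients.* The text does not say so, nor that the site learns the arm. The defect is only that no exemption is stated.
- *The power loss is larger.* On 108 patients the figures would be 71.6% at 5%/1% and 60.9% at 10%/2%. That first removes the unevaluable patients and then subtracts withdrawals from what is left.

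Two further arguments have weight. The toxicity tables in 5.1.1 and 5.1.2 work by holding, reducing or stopping study drug and never call for the code, so unblinding may be rare. Counting discontinuation with a missing outcome as failure is also a recognised and conservative choice, and 6.1 allows a larger sample if more patients are unevaluable for MRI. This limits the size of the problem. It leaves in place the unconditional withdrawal and the conflict within 4.2.3.

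**Conclusion.** The point holds as a defect in a stated rule. Section 4.2.3 ties every code-break to study exit, which can produce missing co-primary outcomes that 6.4.1 counts as failures. It also gives conflicting instructions on non-emergency code-breaks before a locally judged co-primary, and those sentences must be reconciled.

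The bias runs against GDC-0032. It costs power and shrinks the estimate, and does not favour a false positive for the drug. The size is unknown because no unblinding rate is given: under the assumptions above, about 4 points of ORR power at 2%/0% (84.6% to 80.9%) and about 9 at 5%/1% (84.6% to 75.8%). Those figures are upper bounds for the assumed rates, since they take every code-break to precede the MRI and no outcome to be recovered. The case for changing the text rests on the wording and the negligible cost, not on a demonstrated power loss.

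**What to change.** Amend 4.2.3 to state that:

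1. unblinding does not by itself end study participation, and is distinct from stopping blinded treatment;
2. imaging, pathology and follow-up data continue to be collected where those procedures are performed, and the patient is analysed as randomised with her observed outcomes;
3. sponsor code-breaks for regulatory reporting do not trigger withdrawal;
4. non-emergency code-breaks wait until the local pCR result is recorded, which also resolves the conflict with the emergency-only sentence.

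None of this directs whether or when a patient has surgery or any other treatment. Emergency unblinding and treatment decisions are unchanged. The cost is a few sentences, continued data collection in a small number of unblinded patients, and deferral of non-emergency unblinding by some weeks. The loss of response and power attributable to this rule then disappears for every patient whose outcome is obtained.

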4.3 STUDY TREATMENT

4.3.1 Formulation, Packaging, and Handling

4.3.1.1 GDC-0032 and Placebo

GDC-0032 Drug Substance and Drug Product are manufactured according to current Good Manufacturing Practice guidelines for use in the clinical studies. Each lot of

GDC-0032 for clinical studies is subjected to a series of quality control tests to confirm its identity, purity, potency, and quality.

GDC-0032 is provided for use in clinical studies as a white, film-coated, immediate-release tablet formulation of 3 mg strength. The tablet formulation consists of GDC-0032 active, lactose monohydrate, microcrystalline cellulose, croscarmellose sodium, magnesium stearate, and Opadry 2 white film coating. All excipients used in the formulation are compendial (USP/NF/Ph. Eur/JP) grade with the exception of the film-coating. The film-coating consists of polyvinyl alcohol-part hydrolyzed, titanium dioxide, polyethylene glycol 3350, and talc, and these ingredients are compendial.

Placebo tablets will be identical in shape and color to the 3-mg tablets of GDC-0032 and will be indistinguishable from the 3-mg tablets of GDC-0032. The ingredients in the placebo tablets are identical to those in the 3-mg tablets of GDC-0032, except for the absence of GDC-0032 active.

The GDC-0032 active and placebo tablets are packaged in high-density polyethylene bottles, are labeled for clinical use, and should not be stored above 25°C.

For further details, see the GDC-0032 Investigator's Brochure.

4.3.1.2 Letrozole

Letrozole will be labeled according to regulatory requirements in each country, as well as in accordance with International Conference on Harmonisation (ICH) Good Clinical Practice (GCP) and will be labeled for investigational use only. The Sponsor will provide letrozole free of charge to all study sites.

Refer to the letrozole (e.g., Femara[®]) Package Insert or summary of product characteristics (SmPC) for details on the formulation and storage of letrozole.

4.3.2 Dosage, Administration, and Compliance

4.3.2.1 GDC-0032 and Placebo

Patients will receive an oral, daily dose of 6 mg GDC-0032 or placebo on a schedule of 5 days on/2 days off for a maximum of 16 weeks. Patients will take GDC-0032 at the same time of day \pm 2 hours, unless otherwise instructed. Patients will be instructed as to the number of tablets to take. Patients will be asked to record the time and date that they take each dose in a medication diary.

Unless otherwise instructed, GDC-0032 or placebo should be taken on an empty stomach (i.e., approximately 1 hour before or 2 hours after a meal).

If a patient misses a GDC-0032 or placebo dose or vomits up a tablet, she should be instructed to skip that dose and to resume dosing with the next scheduled dose. Missed doses will not be made up. Patients will be instructed to bring their medication diary to

each study visit for assessment of compliance. Patients will also be instructed to bring all unused tablets to each study visit for GDC-0032 or placebo accountability.

Guidelines for dosage modification and treatment interruption or discontinuation are provided in [Section 5.1](#).

Any overdose or incorrect administration of study drug should be noted on the Study Drug Administration eCRF. Adverse events associated with an overdose or incorrect administration of study drug should be recorded on the Adverse Event eCRF.

4.3.2.2 Letrozole

Patients will receive an oral, daily dose of 2.5 mg letrozole for 16 weeks (or until time of surgery at the investigator's discretion). No dose modifications of letrozole are permitted. Any overdose or incorrect administration of letrozole should be noted on the letrozole Administration eCRF. Adverse events associated with an overdose or incorrect administration of letrozole should be recorded on the Adverse Event eCRF.

4.3.3 Investigational Medicinal Product Accountability

All investigational medicinal products (IMPs) required for completion of this study (letrozole and GDC-0032) will be provided by the Sponsor where required by local health authority regulations. The investigational site will acknowledge receipt of IMPs, using the IxRS to confirm the shipment condition and content. Any damaged shipments will be replaced.

IMPs will either be disposed of at the study site according to the study site's institutional standard operating procedure (SOP) or returned to the Sponsor with the appropriate documentation. The site's method of IMP destruction must be agreed to by the Sponsor. The site must obtain written authorization from the Sponsor before any IMP is destroyed, and IMP destruction must be documented on the appropriate form.

Accurate records of all IMPs received at, dispensed from, returned to, and disposed of by the study site should be recorded on the Drug Inventory Log.

4.3.4 Post-Trial Access to GDC-0032

The Sponsor will offer post-trial access to the study drug (GDC-0032, letrozole, or other study interventions) free of charge to eligible patients in accordance with the Roche Global Policy on Continued Access to Investigational Medicinal Product, as outlined below.

A patient will be eligible to receive study drug after the end of the study if all of the following conditions are met:

- The patient has a life-threatening or severe medical condition and requires continued study drug treatment for his or her well-being
- There are no appropriate alternative treatments available to the patient

- The patient and his or her doctor comply with and satisfy any legal or regulatory requirements that apply to them

A patient will not be eligible to receive study drug after the end of the study if any of the following conditions are met:

- The study drug is commercially marketed in the patient's country and is reasonably accessible to the patient (e.g., is covered by the patient's insurance or would not otherwise create a financial hardship for the patient)
- The Sponsor has discontinued development of the study drug or data suggest that the study drug is not effective for untreated, postmenopausal ER+/HER2-, early stage, operable breast cancer
- The Sponsor has reasonable safety concerns regarding the study drug as treatment for untreated, postmenopausal postmenopausal ER+/HER2-, early stage, operable breast cancer
- Provision of study drug is not permitted under the laws and regulations of the patient's country

The Roche Global Policy on Continued Access to Investigational Medicinal Product is available at

http://www.roche.com/policy_continued_access_to_investigational_medicines.pdf.

